8.3 ANALYSIS POPULATIONS

The following populations will be assessed:

Safety Population (SP):	All randomized patients who receive at least one dose of the study drug. Patients will be analyzed according to the treatment received. All safety analyses will be based on the Safety Population.
Full Analysis Set (FAS):	All randomized and treated patients who had the baseline assessment and at least one post randomization assessment of the primary efficacy measure of weekly SBM frequency. The FAS is the main population for assessments of efficacy.
Per Protocol (PP) Population:	All patients in the FAS population who complete the 4-week Treatment Period or discontinue from study treatment due to adverse event(s) or lack of efficacy, with the exception of major protocol violators. Criteria to identify

the PP population will be detailed in the SAP. Decisions regarding exclusion from the PP Population will be made prior to unblinding the database.

Efficacy analyses will be based on the FAS Population. Efficacy analyses will be repeated for the PP Population to assess the sensitivity of the analyses to the choice of analysis set.

Deviations from the study protocol, including violations of inclusion/exclusion criteria, will be assessed as “minor” or “major.”. Major deviations from the protocol will lead to the exclusion of a patient from the PP Population and will be determined prior to unblinding the study database. Missed telephone contact (TC) visits will not be considered deviations from the study protocol.

8.4 GENERAL CONSIDERATIONS

The final data analysis will be performed after all patients have either completed or have been discontinued from the study. The study will be unblinded after patient membership in each of the various analysis populations has been determined at a blinded data review meeting and upon confirmation of database lock.

Three treatment groups are identified for all analyses cited in the following as “by treatment group”: A (patients in Age Group A receiving plecanatide doses of 0.5 mg or 1.0 mg); B (patients in Age Group B receiving plecanatide doses of 1.0 mg, 2.0 mg, or 3.0 mg); Placebo (all patients randomized to receive placebo.)

Any deviations from the analyses presented here will be detailed in the clinical study report. All outputs will be produced using SAS® version 9.2 or later.

All efficacy data will be summarized and analyzed using the FAS and PP Populations unless otherwise noted. Safety data will be summarized using the Safety Population.

Imputation of missing data, where appropriate, will be performed as indicated for a given analysis. Any spurious or erroneous data will be queried and followed up until satisfactorily resolved; if not resolvable, the data will be set to missing. All data collected in the clinical database will be included in the data listings.

Summary statistics—number of patients (n), mean, standard deviation (SD), median, minimum, and maximum—will be presented for continuous variables. Frequencies and percentages will be presented for categorical variables. Unless otherwise noted, percentages will be calculated using the total number of patients in the appropriate population and/or subgroup and per treatment group where applicable. Where data are collected over time, both the observed data and change from the Screening Period (baseline) will be summarized at each time point.

Statistical testing including p-values and confidence intervals (CIs) will be presented as described in each section below. The Type I error rate (alpha) for the analysis of the primary efficacy endpoint is 0.05 (two-sided).

8.4.1 Missing Data Conventions

Missing values of safety parameters will not be imputed.

The weekly BM (SBM, CSBM) rate is the sum of the BMs (SBMs, CSBMs) recorded for the days in the week for which a BM response is recorded in the daily diary. Note that this is equivalent to a “worst case” analysis in that the BM (SBM, CSBM) rate for the week is the sum of the BMs (SBMs, CSBMs) recorded for the days in the week for which BMs were reported, plus 0 BMs (SBMs, CSBMs) for each day in the week for which the BM response is missing. In any week in which no BM response is recorded, the weekly BM (SBM, CSBM) rate will be set to 0 in any summary or linear mixed-effects model analysis involving

the weekly BM (SBM, CSBM) rate. In particular, for a randomized patient who withdraws from study participation prior to the end of the study, the patient is considered to have a weekly BM (SBM, CSBM) rate equal to 0 for any weeks remaining in the planned duration of the study for which the patient has no BM responses recorded.

The weekly average IBS-related daily abdominal pain score is the average of the non-missing, abdominal pain scores recorded in that week, i.e., the weekly average is the sum of the abdominal pain scores recorded in the diary in the given week, divided by the number of pain scores recorded in the week. In any week in which a patient has no diary days for which an abdominal pain score is recorded, the weekly average abdominal pain score will be set to missing. In any linear mixed-effects model analysis involving the weekly average abdominal pain score, if the average score is set to missing in a given week, it will be left as missing in the linear model. In particular, for a randomized patient who withdraws from study participation prior to the end of the study, the weekly average abdominal pain score will be set to missing for any weeks remaining in the planned duration of the study for which the patient has no abdominal pain data.

In any analysis of the frequency of fecal incontinence, the frequency of defecation pain, and the frequency of large diameter stools will follow the same methodology as described above for the determination and analysis of the weekly BM rate.

In any analysis involving the severity of defecation pain, the determination of weekly averages will follow the same methodology as described above for the abdominal pain score. That is, the weekly average item score is the sum of the non-missing item scores recorded during the week, divided by the total number of non-missing item scores recorded. In any week in which a patient has no non-missing item scores recorded, the weekly average score will be set to missing in any summary or linear mixed-effects model analysis involving the weekly average item score.

In any analysis involving stool consistency (mBSFS-C scores or BSFS scores), the determination of weekly averages will follow the same methodology as presented above for abdominal pain.

However, since stool consistency cannot be assessed if the patient does not have at least one SBM during the week in question (i.e., stool consistency is based on SBMs only), the weekly average will also be set to missing if no SBMs are recorded for any days in the week. Also, it is possible that a patient has no baseline weekly average stool consistency score because of the SBM criterion; in that case the patient will be excluded from any change from baseline analyses of stool consistency.

8.4.2 Diary Data Visit Windows

The daily electronic diary entries reported during the Treatment Period will be classified into 4 weeks as follows:

- Day 1-7 = Week 1
- Day 8-14 = Week 2
- Day 15-21 = Week 3
- Day 22-28 = Week 4

Non-diary data, such as vital signs, clinical laboratory assessments, will be displayed and analyzed according to the nominal visit date on the eCRF. Assessments taken outside of protocol allowable windows for nominal visits will be displayed according to the slotting scheme presented in the SAP for unscheduled or out-of-window visits.

8.4.3 Baseline Definition

For each safety parameter, the most recent valid assessment recorded before randomization will be used as the baseline for all analyses of that safety parameter.

For efficacy parameters, the baseline values will be derived from data collected in the 2-week electronic diary assessment at the end of the Screening Period (baseline). The last 14 days of diary entries prior to Day 1 will be the default standard for derivation of these values.

The baseline BM (SBM, CSBM) weekly rate will be the weekly average number of BMs (SBMs, CSBMs) recorded during the 2-week baseline assessment period; similarly, for frequency of abdominal pain and abdominal discomfort, frequency of fecal incontinence, frequency of defecation pain, and frequency of large diameter stools. Baseline stool consistency, severity of abdominal pain, abdominal discomfort, and severity of defecation pain will be calculated as follows: for each week of the baseline assessment, the weekly average is the sum of the non-missing scores recorded during the week divided by the total number of non-missing scores recorded during that week; the baseline is then equal to one-half of the sum of the two weekly average scores.

8.5 DISPOSITION OF PATIENTS

Patient disposition and reasons for discontinuation from the Treatment Period of the study will be summarized by treatment group for all randomized patients.

8.6 TREATMENT COMPLIANCE

Dosing compliance will be defined by the dosing compliance ratio: the number of doses actually taken by the patient divided by the number of doses that were expected to be taken during the same period multiplied by 100. Treatment compliance is defined as taking equal to or greater than 80% of the drug dosage prescribed. Otherwise, the patient will be considered noncompliant with study treatment. Rates of treatment compliance as defined above will be compared between treatment groups using the Chi-square test.

Patient compliance with making daily electronic diary entries is monitored by the IWRS; patients non-compliant in making daily diary entries will be withdrawn from the study.

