3.1 INCLUSION CRITERIA

A patient will be eligible for study participation if he or she meets all of the following criteria:

1. Male or female child or adolescent age 6 to < 18;
2. Meets ROME IV criteria for child/adolescent IBS-C defined as:
For at least 2 months before diagnosis the patient has had:
 1. Abdominal pain at least 4 days per month associated with one or more of the following:
 - a. Related to defecation
 - b. A change in frequency of stool
 - c. A change in form (appearance) of stool;
 2. The pain does not resolve with resolution of the constipation (children in whom the pain resolves have functional constipation, not irritable bowel syndrome);
 3. After appropriate evaluation, the symptoms cannot be fully explained by another medical condition
 4. More than one-fourth (25%) of bowel movements with Bristol stool form types 1 or 2 and less than one-fourth (25%) of bowel movements with Bristol stool form types 6 or 7 on the BSFS or 4 or 5 on the mBSFS-C;
3. Patient's parent/guardian/LAR is able to voluntarily provide written, signed, and dated consent and patient is able to voluntarily provide assent as per IRB guidance;
4. Patient and patient's parent/guardian/LAR demonstrates an understanding, ability, and willingness to fully comply with protocol requirements and study procedures (e.g., acceptance of venipuncture, acceptance of urine drug screen for opiates, visit schedule, complete daily electronic diary reporting).

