***Soiling of underwear in younger children may be indicative of Fecal Incontinence**

To remain eligible for the study, patients must complete at least 5 of the 7 days of electronic End-of-Day diary entries for each of the 2 weeks of Baseline diary period.

Compliance with diary entries should be a focus for patient education at the telephone contact visits and as needed per the judgement of the clinical site staff.

The following endpoints will be assessed using data collected via the electronic diary in “real time”:

• *Frequency of Bowel Movements*

Patients/caregivers will be asked to report each BM experienced.

• *Stool Consistency*

Patients/caregivers will be asked to rate the patient’s stool consistency according to the BSFS (see **Appendix C**) or mBSFS-C (see **Appendix D**), which will be provided to them in the form of a laminated card (and will appear on the appropriate electronic device) at the Screening Visit (Visit 1), and may be referred to as often as necessary throughout the Screening, Treatment and Post-treatment Periods. The BSFS and mBSFS-C are validated measures of stool consistency commonly used in clinical trials.

• *Stool Diameter*

Patients/caregivers will be asked to report the number of large diameter stools. A large diameter stool is defined as one that is large enough to clog the toilet.

• *Use of Rescue Medication (RM)*

Patients/caregivers will report the use of provided rescue medication (Dulcolax®), including time of use and amount of rescue medication used. Use of rescue medication will determine whether a BM was spontaneous, but only this aspect of rescue medication use is part of the primary endpoint.

The following endpoints will be assessed using data collected via the electronic diary at the end of the day:

• *Fecal Incontinence*

As part of the daily diary (end of day), the following question will be asked:

How many episodes of fecal incontinence did you experience today?

0 1 2 3 more than 3

• *IBS Symptoms*

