5.2.8 Early Withdrawal/Early Termination Visit (EW/ET)

Patients are free to withdraw from participation in the study at any time. Investigators may choose to discontinue a patient's participation in the study if they believe it is in the patient's best interest clinically. If a patient's post-randomization compliance is of concern, contact the medical monitor to discuss. If the patient has an intervening illness that requires discontinuation of study participation, the patient and Investigator will follow procedures for early withdrawal. The following are examples of AEs that qualify for Early Withdrawal (EW):

- A positive pregnancy test will require discontinuation from the study (see **Section 7.7**).
- Changes in laboratory values, PE findings, or other assessments considered by the Investigator (or designee) to be clinically significant will require discontinuation from the study.
- Clinically significant TEAEs, including clinically significant laboratory test abnormalities or SAEs regardless of relatedness to study treatment that cause the patient, investigator, or Sponsor to feel it is not in the patient's best interest to continue.

A patient may also be withdrawn from study drug/study by the Sponsor, regulatory authorities, or the institutional review board (IRB). Patients will also be withdrawn if the entire study is terminated prematurely as described in **Section 9.9**.

Patients who discontinue early from the study should, if possible, have an Early Withdrawal Visit. The Investigator must make every effort (with proper documentation) to have the patient complete this final visit. This visit should take place as soon as possible (and within 5 days) after the patient stops taking study drug.

The following procedures will be performed at the Early Withdrawal Visit:

- Collect/record unused study drug from the supply dispensed at the previous visit
- Have the patient/caregiver complete the PRO questionnaires (see Study Procedure Manual)
- Assess/record changes in concomitant medications and diet
- Symptoms directed physical examination and vital signs (seated blood pressure, heart rate, respiration, and body temperature)
- Safety laboratory assessments (hematology, serum chemistry, urinalysis)
- Perform urine pregnancy test, if applicable
- Collect blood samples for plecanatide/SP-338 assessments
- Assess adverse events.

In all cases, a single, primary reason for withdrawal must be recorded on the eCRF.

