6.7 COMPLIANCE

Patients will be advised as to how to take their daily medication and will return all unused study drug to the clinical site at the end of the Treatment Period or Early Withdrawal Visit. The number of remaining tablets will be counted and entered into IWRS for that patient. Patients unwilling or unable to maintain compliance with study drug administration or procedures may be discontinued from the study at the discretion of the investigator in conjunction with the medical monitor.

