4.2. PER PROTOCOL (PP) POPULATION

All subjects in the FAS population who complete the 4-week Treatment Period or discontinue from study treatment due to adverse event(s) or lack of efficacy, with the exception of major protocol violators. If a diary compliance is < 70% or treatment compliance is < 80% then the subject is excluded from the PP Population. Subjects with Week 4 visit outside of the window 28 +/- 3 (study days 25 to 31) days will be excluded from the PP Population. Final decisions regarding exclusion from the PP Population will be made prior to unblinding the database.

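### Protocol 8.6 withdraws patients outright for poor diary compliance, with no threshold and against 5.2.8 and 6.7; diary data they would still have given then enter the primary analysis as zeros

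*Combined protocol and SAP*

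**What the plan says.** Protocol 8.6 has the IWRS monitor diary entries and then states that "patients non-compliant in making daily diary entries will be withdrawn from the study". It gives no percentage, no time window and no role for judgement.

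Other sections treat the same matter differently:

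- Protocol 5.2.8: where a patient's "post-randomization compliance is of concern, contact the medical monitor to discuss".
- Protocol 6.7: patients who do not keep to study drug or procedures "may be discontinued from the study at the discretion of the investigator in conjunction with the medical monitor". Inclusion criterion 4 (Protocol 3.1) gives "complete daily electronic diary reporting" as an example of those requirements and procedures, so 6.7 covers diary lapses.
- Protocol 4.2.1: "Compliance with diary entries should be a focus for patient education at the telephone contact visits".
- SAP 4.2: "If a diary compliance is < 70% or treatment compliance is < 80% then the subject is excluded from the PP Population".

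The only diary threshold for staying in the study is also in Protocol 4.2.1: "patients must complete at least 5 of the 7 days of electronic End-of-Day diary entries". It applies to the two baseline weeks only.

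On the data that follow a withdrawal, Protocol 8.4.1 says that "the patient is considered to have a weekly BM (SBM, CSBM) rate equal to 0 for any weeks remaining" in which no response is recorded. SAP 3.3.4 keeps this rule. Withdrawn patients are not replaced (Protocol 5.2.8).

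**The concern.** A site facing a randomised patient who misses entries has three instructions: withdraw, discuss, or decide at discretion. It cannot follow all of them, and two sites could treat the same lapse differently.

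The consequence reaches the primary endpoint. The Early Withdrawal procedures in 5.2.8 include no further diary entries, so withdrawal ends diary collection. Each remaining treatment week then becomes 0 SBMs in the Full Analysis Set (FAS) model. A patient who misses some days but would have kept reporting on others loses all later information and is scored as having no bowel movements. If such withdrawals are equally common in both arms, the treatment difference shrinks. If they are not, the difference is biased in a direction that cannot be known beforehand.

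**Working it through.** **Wording.** Protocol 8.6 does not say randomised. It sits under Treatment Compliance, however, and patients who fail before randomisation are called screen failures (Protocol 5.2.1 and 5.2.2). The post-randomisation reading is therefore the natural one. On that reading, a mandatory rule in 8.6 stands against a discussion rule in 5.2.8 and a discretionary rule in 6.7. SAP 5.1.3 does not repeat the sentence, but under Protocol 8 the SAP supersedes the protocol only for analyses, so 8.6 still governs conduct.

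**Inputs from the plan.** Difference 1.5; SDs 3.5 (plecanatide) and 2.3 (placebo); 102 and 34 patients (Protocol 8.2, SAP 3.1). Two-sided alpha 0.05 (Protocol 8.4; the 0.05% printed in 8.2 is a misprint). Planned Group B sizes 90 and 30 (Protocol Table 3). Four treatment weeks (Protocol 8.4.2).

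**The plan's own figure.** Two-sample z-test with unequal variances:

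- 102 and 34: Φ(1.5/√(3.5²/102 + 2.3²/34) − 1.96) = Φ(1.5/0.525 − 1.96) = 81.5%, as stated.
- 90 and 30: Φ(1.5/0.559 − 1.96) = 76.5%.

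**Assumptions, none of them in the documents.** A fraction d of an arm is withdrawn for diary lapses and a fraction f of its four weeks is lost. Baseline B is 3 SBM/week, with range 2 to 4 (exclusion 21 caps each baseline week at 6). A share r of the later entries would have been made had the patient stayed.

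**One patient.** Baseline 3, true change +2, full entries in Weeks 1 and 2, withdrawn after Week 2 (f = 0.5):

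- Scored change: (2 + 2 − 3 − 3)/4 = −0.5 instead of +2.
- Shift: −2.5, which equals −f × (B + change) = −0.5 × 5.

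**One arm only, d = 10%.**

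- Arm mean shift: 0.10 × (−2.5) = −0.25 SBM/week, or −0.20 at baseline 2 and −0.30 at baseline 4.
- This takes r = 1. The part due to withdrawal is −0.25 × r: −0.125 at r = 0.5, and nothing at r = 0, because a patient who has stopped reporting is scored 0 whether withdrawn or not.

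**Both arms, d = 10%, r = 1, equal baselines.** The difference becomes 1.5 × (1 − d × f):

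- After Week 2: 1.5 × (1 − 0.10 × 0.5) = 1.425, a 5% loss.
- After Week 1: 1.5 × (1 − 0.10 × 0.75) = 1.39.
- Power at 90 and 30, using the mixture mean and SD and further assuming changes of +1.0 (placebo) and +2.5 (plecanatide) and a baseline SD of 1.5: 71% to 74% after Week 2 and 64% to 70% after Week 1, against 76.5% with no withdrawals.

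**Unequal rates, same assumed changes.** Difference = 1.5 − f × [d(plecanatide) × (2.5 + B) − d(placebo) × (1.0 + B)], over B = 2 to 4 and f = 0.5 to 0.75:

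- 20% plecanatide, 10% placebo: 0.90 to 1.20.
- 5% plecanatide, 15% placebo: 1.61 to 1.82.

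**The case against.** The strongest reply is that the damage comes from the zero rule, not from 8.6. Every missed day and every empty week counts as 0 whether or not the patient is withdrawn, so a child who stops reporting gets the same zeros while enrolled. That stands. Section 8.6 adds harm only through entries that would still have been made.

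Four stronger readings are tempting, and the documents do not support them.

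- A reader might infer that SAP 4.2 flatly contradicts 8.6. It does not. A withdrawn patient with one post-randomisation SBM assessment also stays in the FAS (SAP 4.1). The 70% exclusion could still act on patients who stop for adverse events or lack of efficacy. Because 8.6 has no threshold, no strict conflict can be shown. The two fit awkwardly: a patient withdrawn for diary lapses already falls outside the Per Protocol (PP) population, so the cut-off has most to do if poor reporters stay.
- A reader might take 0.25/1.5 = 17% as the bias. That needs 10% affected in one arm and none in the other, complete entries in Weeks 1 and 2 from a patient withdrawn for missing entries, and full reporting afterwards.
- A reader might infer that all outcome collection ends. The Early Withdrawal Visit still collects questionnaires, laboratory tests, pharmacokinetic samples and adverse events. What is lost is later diary data.
- A reader might infer that every withdrawn patient is scored zero. One with no post-randomisation SBM assessment leaves the FAS instead.

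Reminders and site calls should limit lapses. The PP repeat gives a check without these zeros, though an imperfect one, because it drops the patients concerned.

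**Conclusion.** The conflict between Protocol 8.6 and Protocol 5.2.8 and 6.7 is real, on the reading that 8.6 applies after randomisation, and 8.6 lacks a threshold. The tension with SAP 4.2 is implied only. As written, 8.6 worsens the primary data by cutting off diary entries that the zero rule then replaces with the worst value.

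The size is not fixed by the documents. With equal 10% withdrawal after Week 2 and full reporting otherwise, the loss is about 5% of the planned difference. With one arm affected, that arm moves by up to about 0.25 SBM/week under the stated assumptions, and less if the patients would have reported only partly. The direction under unequal rates is open. The sponsor should correct this; the figures do not show that the primary comparison is invalid.

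**What to change.** Reconcile Protocol 8.6 with 5.2.8 and 6.7, so that a diary lapse does not automatically end study participation and the three sections give sites one instruction. Define what counts as diary non-compliance after randomisation. State that diary and visit data collection continues to Day 42 for every randomised patient who agrees, whether or not study drug continues. Whether study drug is stopped is for the sponsor to settle when reconciling those sections; no rule is proposed here.

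This does not cure the zero-imputation rule in Protocol 8.4.1 and SAP 3.3.4. That rule also affects missed days in patients who stay, and needs its own correction.

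The cost is short edits to the three sections and some continued follow-up of poor reporters, using the reminders and calls already planned.
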